# **Clinical Study Protocol**

## **Johnson & Johnson Vision**

### **Exclusion Criteria at Baseline Evaluation**

The subject must not:

9. Have clinically significant (grade 3 or higher on the FDA grading scale) slit lamp findings (e.g., corneal edema, neovascularization or staining, tarsal abnormalities or bulbar injection) or other corneal or ocular disease or abnormalities that the investigator believes might contraindicate contact lens wear or may otherwise compromise study endpoints (including entropion, ectropion, chalazia, recurrent styes, glaucoma, history of recurrent corneal erosions, aphakia, moderate or above corneal distortion, herpetic keratitis).
10. Have a history of strabismus or amblyopia.
11. Have fluctuations in vision due to clinically significant dry eye or other ocular conditions.
12. Have had or have planned (within the study period) any ocular or intraocular surgery (e.g., radial keratotomy, PRK, LASIK, iridotomy, retinal laser photocoagulation, etc.).

### **3.4. Enrollment Strategy**

Study subjects will be recruited from the Institution/clinical site's subject database and/or utilizing Independent Ethics Committee (IEC) or Institutional Review Board (IRB) approved materials.

## **4. STUDY DESIGN AND RATIONALE**

### **4.1. Description of Study Design**

The study is a 2-phase, single-site, non-dispensing, controlled, randomized, double-masked, 2x2 crossover (2 study lenses x 2 wearing periods) design where one of the study lenses will be worn bilaterally for 2.5-3 hours on Visit 1 and the other study lens worn bilaterally for 2.5-3 hours on Visit 2. At study closure, participants will have no further access to the study lenses.

It is important that the subjects wear the same type of lens on both eyes (i.e., both eyes wear spherical, both eyes wear multifocal, or both eyes wear toric). All lenses will be fit for distance vision OD and OS according to the fitting guides located in the appendices, which largely follow the Fitting Guide of the control lenses.

Non-presbyopes (age 18 through 39) may wear either a spherical lens or a toric lens on both eyes. The Fitting Guide for spherical products extends to 1.00 D of refractive cylinder, while the Fitting Guide for toric products starts at 0.75 D of refractive cylinder. The investigator will therefore use her / his experience in deciding whether the subject will be best fit in a spherical or toric lens on each eye. If fitting the toric lens, the refractive cylinder power should be suitable to be fit with either the 0.75 D or 1.25 D cylinder lens.

Presbyopes (age 40-70) will be fit with a multifocal lens on both eyes. Note that the multifocal lenses, particularly the higher ADD powers, are likely to over-refract needing more minus. This is normal and will not follow the same 0.00 D over-refraction requirement as the spherical and toric designs.

# **Clinical Study Protocol**

## **Johnson & Johnson Vision**

### **4.2. Study Design Rationale**

The purpose of this study is to evaluate the performance of a new UV/HEV-filter in a 2x2 crossover design for three different subject groups (i.e., sphere wears, multifocal wears, and toric wears). Crossover designs are a well-established study design in which subjects are exposed to multiple treatments during different time periods. This design is cost effective and more efficient since it eliminates part of the inter-subject variability from the treatment comparisons. Subjects will be randomized into the two lens wear sequences: Test/Control or Control/Test. Randomization eliminates selection bias and balances both the known and unknown confounding factors that may affect the study outcomes. A potential limitation of crossover design is the carry-over effect from the previous treatment. The 2 study periods (visits) will be separated by 1-14 days and the wearing time of 2.5-3 hours in each period is considered effectively short to minimize the presence of the carry-over effect in the psychometric tests of interest. Rest period between trials within a single measurement type and between different measurement types is incorporated to eliminate the impact of any previous testing.

- Within a single measurement type (e.g., visual range), a minimum of 30-seconds will be taken between trials.
- Between measurement types (e.g., when switching from visual range to measuring brightness perception), a 5-minute break will be taken.
- Participants will be given a 15-minute break after every 45 minutes of visual function testing.

### **4.3. Enrollment Target and Study Duration**

#### Phase 1

Phase 1 will have an enrollment target of 24 subjects, with a target of at least 20 to complete. Approximately 10 subjects will wear spherical soft contact lenses and approximately 10 subjects will wear multifocal soft contact lenses. The study will be conducted at a single clinical site. A subject will be considered enrolled upon signing the informed consent form.

There will be 2 visits in total per subject separated by 1-14 days. The enrollment period is 2 weeks making the duration of Phase 1 approximately 4 weeks. If subjects discontinue prior to the final evaluation, then additional subjects may be enrolled at the discretion of the study sponsor to maintain sample size requirements.

#### Phase 2

Phase 1 results are used to estimate the number of subjects required for Phase 2. However, the total sample size for Phase 2 will be approximately 135 subjects due to resources and study timing. The study will be conducted at a single clinical site. A subject will be considered enrolled upon signing the informed consent form. Phase 1 subjects will not be Phase 2 subjects.

There will be 2 visits in total per subject separated by 1-14 days. The enrollment period is 12 weeks making the duration of Phase 2 approximately 14 weeks. If subjects discontinue prior to the final evaluation, then additional subjects may be enrolled at the discretion of the study

# **Clinical Study Protocol**

## **Johnson & Johnson Vision**

sponsor to maintain sample size requirements. The investigation will end at the time that the study data is hard locked.

### **5. TEST ARTICLE ALLOCATION AND MASKING**

#### **5.1. Test Article Allocation**

This is a two phase, 2x2 crossover study within each phase. Both study lenses will be worn in a bilateral and randomized fashion. Randomly-permuted block randomization will be used to avoid bias in the assignment of subjects to treatment and to enhance the validity of statistical comparisons across treatment groups. A computer-generated randomization scheme will be used to randomly assign subjects to one of the two possible lens wear sequences (Test/Control or Control/Test) within each study phase. The randomization will be stratified by subject group within each phase. The random scheme will be generated by the unmasked biostatistician using the PROC PLAN procedure in Statistical Analysis System (SAS) Software Version 9.4 or higher (SAS Institute, Cary, NC).

Randomization will be performed at Visit 1. The following must have occurred prior to randomization:

- Informed consent must have been obtained.
- The subject must have met all eligibility criteria.
- The subject's screening and baseline information must have been collected.

#### **5.2. Masking**

This is a double-masked study. Subjects will be unaware of the identity of the investigational product. The investigator conducting the psychophysical testing will also not be informed. Instead, lens type will be identified by code only, and the link between the code and the lens type will not be revealed to the investigator conducting the psychophysical testing until after the database has been locked. The clinician fitting the lenses will not be masked as to the identity of the investigational products and may be able to tell the difference between the Test and Control lenses based on color differences between the lenses.

#### **5.3. Procedures for Maintaining and Breaking the Masking**

Every attempt will be made to keep the clinical trial personnel involved in the study (e.g. data management, study lead biostatistician and clinical operations) unaware of the identity of the assigned study lenses. The identity of the study lenses will be masked by having the blister packs labeled with the study number, lot number, sphere power, expiration date and the randomization codes. Only the unmasked biostatistician generating the lens fitting schedule will have access to the decode information that allows matching of the randomization codes to the test articles. The medical monitor will also have access to the decode information in case breaking the mask is necessary for the urgent medical treatment of a subject.

Under normal circumstances, the mask should not be broken until all subjects have completed the study and the database is finalized. Otherwise, the mask should be broken only if specific

# Clinical Study Protocol

## Johnson & Johnson Vision

emergency treatment/course of action would be dictated by knowing the treatment status of the subject. In such cases, the investigator may, in an emergency, contact the medical monitor. In the event the mask is broken, the sponsor must be informed as soon as possible. The date, time, and reason for the unmasking must be documented in the subject record. The investigator is also advised not to reveal the study treatment assignment to the clinical site or sponsor personnel.

Subjects who have had their treatment assignment unmasked are expected to return for all remaining scheduled evaluations.

## 6. STUDY INTERVENTION

### 6.1. Identity of Test Articles

The following contact lenses will be used in this study:

Table 1: Test Articles

	Test - Sphere	Test - Multifocal	Test - Astigmatism
Name	ACUVUE® OASYS MAX 1-Day	ACUVUE® OASYS MAX 1-Day Multifocal	TRA
Manufacturer	JJVC	JJVC	JJVC
Lens Material	senofilcon A	senofilcon A	senofilcon A
Nominal Base Curve @ 22°C	8.5	8.3	8.5
Nominal Diameter @ 22°C	14.3	14.3	14.3
Nominal Distance Powers (D)	-1.00 through -6.00 in 0.25 steps	-1.00 through -6.00 in 0.25 steps	-1.50 through -4.00 in 0.25 steps
Nominal ADD Powers	NA	Low, Med, High	NA
Nominal Cylinder Powers (D)	NA	NA	-0.75, -1.25
Nominal Cylinder Axes (degrees)	NA	NA	10, 80, 90, 100, 170, 180
Water Content (Optional)	38	38	38
Oxygen Permeability (Dk)	103	103	103
Wear Schedule in Current Study	Daily	Daily	Daily
Replacement Frequency	Daily	Daily	Daily
Packaging Form (vial, blister, etc.)	Blister	Blister	Blister
New UV/HEV-filter	Yes	Yes	Yes

**Clinical Study Protocol**  
**Johnson & Johnson Vision**

Table 2: Control Articles

	Control - Sphere	Control - Multifocal	Control - Astigmatism
Name	ACUVUE® OASYS 1-Day	ACUVUE® OASYS Multifocal	ACUVUE® OASYS 1-Day for Astigmatism
Manufacturer	JJVC	JJVC	JJVC
Lens Material	senofilcon A	senofilcon A	senofilcon A
Nominal Base Curve @ 22°C (mm)	8.5	8.4	8.5
Nominal Diameter @ 22°C (mm)	14.3	14.3	14.3
Nominal Distance Powers (D)	-1.00 through -6.00 in 0.25 steps	-1.00 through -6.00 in 0.25 steps	-1.50 through -4.00 in 0.25 steps
Nominal ADD Powers	NA	Low, Med, High	NA
Nominal Cylinder Powers (D)	NA	NA	-0.75, -1.25
Nominal Cylinder Axes (degrees)	NA	NA	10, 80, 90, 100, 170, 180
Water Content ( Optional )	38	38	38
Oxygen Permeability (Dk)	103	103	103
Wear Schedule in Current Study	Daily	Daily	Daily
Replacement Frequency	Daily	Daily	Daily
Packaging Form (vial, blister, etc.)	Blister	Blister	Blister
New UV/HEV-filter	Yes	Yes	Yes

Based on estimates from the CLIFT program, this study will utilize a minimum of 36 lenses per SKU for sphere, a minimum of 14 lenses per SKU for multifocal, and a minimum of 20 lenses per SKU for astigmatism.

# **Clinical Study Protocol**

## **Johnson & Johnson Vision**

### **6.2. Ancillary Supplies/Products**

The following solutions will be used in this study:

Table 3: Ancillary Supplies

Solutions				
Solution Name/Description	Acuvue™ RevitaLens Multipurpose Solution	Single use Eye-Cept® Rewetting Drops	LaciPure Saline Solution	ScleralFil Preservative Free Saline Solution
Manufacturer	Johnson & Johnson Vision	Optics Laboratory	Menicon	Bausch & Lomb
Preservative	alexidine dihydrochloride 0.00016% and polyquaternium-1 0.0003%	None	None	None

Lens cases and fluorescein strips (either 0.6 mg or 1.0 mg) will be supplied for use as needed.

### **6.3. Administration of Test Articles**

Test articles will be dispensed to subjects meeting all eligibility requirements, including any dispensing requirements set forth in this clinical protocol. Subjects will be dispensed an adequate supply of test articles to complete the study. Lost or damaged test articles may be replaced at the discretion of the investigator and/or the sponsor.

### **6.4. Packaging and Labeling**

The test articles will be packaged in blisters as the primary packaging. The test article will be over-labeled to mask the subject and investigators to the identity of the lens. The test articles will be in investigational cartons sealed with a tamper evident seal plastic bags as the secondary packaging form. Sample labels for each lens type are shown below. The information represented on the labels below are sample information only and are not representative of the actual study lens information.

# Clinical Study Protocol

## Johnson & Johnson Vision

Table 4: Sample Labels

Sphere Label	Multifocal Label	Astigmatism Label	Secondary Label (Sphere, Multifocal, and Astigmatism)

CAUTION: INVESTIGATIONAL DEVICE LIMITED BY U.S. LAW TO INVESTIGATIONAL USE EXCLUSIVELY FOR CLINICAL INVESTIGATIONS
 
Contents: One contact lens in solution.
   
LOT C7VN01 SPH -1.25 ADD HGH EXP 2025/08/01 CR-6480 RC P
	
CAUTION: INVESTIGATIONAL DEVICE LIMITED BY U.S. LAW TO INVESTIGATIONAL USE EXCLUSIVELY FOR CLINICAL INVESTIGATIONS
 
Contents: One contact lens in solution.
   
LOT C7M101 SPH -1.00 EXP 2023/03/15 CR-6480 RC P
	
CAUTION: INVESTIGATIONAL DEVICE LIMITED BY U.S. LAW TO INVESTIGATIONAL USE EXCLUSIVELY FOR CLINICAL INVESTIGATIONS
 
Contents: One contact lens in solution.
   
LOT C7G201 SPH -4.00 CYL -0.75 AXIS 180 EXP 2023/03/15 CR-6480 RC P
	
Sponsored By/Parrainé par:
 
Johnson & Johnson Vision Care, Inc. [name] [name], USA
 
Contents/Contenu:
 
Contact Lenses in Solution Lentilles cornéennes dans une solution

### 6.5. Storage Conditions

Test articles will be maintained at ambient temperatures at the clinical site. Test articles must be kept under secure conditions.

### 6.6. Collection and Storage of Samples

When possible, any lens or test article associated with an Adverse Event and/or a Product Quality Complaint must be retained and stored in a glass vial with moderate solution pending directions from the sponsor for potential return to JJVC.

### 6.7. Accountability of Test Articles

JJVC will provide the Investigator with sufficient quantities of study articles and supplies to complete the investigation. The Investigator is asked to retain all lens shipment documentation for the test article accountability records.

Test articles must be kept in a locked storage cabinet, accessible only to those assigned by the Investigator for dispensing. The Investigator may delegate this activity to authorized study site personnel listed on the Site Delegation Log. All test articles must be accounted. This includes:

1. What was dispensed for the subject for trial fitting, to wear out of the office, or issued for the subject to replace appropriately between visits.
2. What was returned to the Investigator unused, including expired or malfunctioning product.
3. The number and reason for unplanned replacements.

The Investigator will collect all unused test articles from the subjects at the end of the subject's participation. Subject returned unused test articles must be separated from the clinical study inventory of un-dispensed test articles and must be labeled with the subject number and date of return. Following final reconciliation of test articles by the monitor, the Investigator or monitor will return all unused test articles to JJVC.

# Clinical Study Protocol

## Johnson & Johnson Vision

If there is a discrepancy between the shipment documents and the contents, contact the study monitor immediately.

## 7. STUDY EVALUATIONS

### 7.1. Time and Event Schedule

Table 5: Time and Events: Phase 1 and Phase 2

Visit Information	Visit 1 Screening, Baseline, Treatment 1 Fit and Evaluation	Visit 2 Treatment 2 Fit and Evaluation, Final Evaluation
Time Point	Day 0	1-14 days following Visit 1
Minimum lens wear time immediately prior to visit	NA	NA
Estimated Visit Duration	3.0 hours	2.5 hours
Statement of Informed Consent	x	
Demographics	x	
Medical History/Concomitant Medications	x	x
Habitual Contact Lens Information	x	
Eligibility Following Screening	x	
Entrance Visual Acuity	x	
Subjective Sphero-Cylindrical Refraction and best-corrected VA	x	
Entrance Slit Lamp Biomicroscopy	x	x
Eligibility Following Baseline Evaluation	x	
Lens Selection	x	
Lens Insertion & Settling	x	
Visual Acuity and Over Refraction	x	x
Lens Power Modification (if applicable)	x	
Subject Reported Ocular Symptoms	x	x
General Fit Assessment	x	x
Toric Fit Assessment (if applicable)	x	
Psychophysical Testing: Visual Range	x	x
Psychophysical Testing: Brightness Perception	x	x

# Clinical Study Protocol

## Johnson & Johnson Vision

Visit Information	Visit 1 Screening, Baseline, Treatment 1 Fit and Evaluation	Visit 2 Treatment 2 Fit and Evaluation, Final Evaluation
Time Point	Day 0	1-14 days following Visit 1
Minimum lens wear time immediately prior to visit	NA	NA
Estimated Visit Duration	3.0 hours	2.5 hours
Psychophysical Testing: Motion Detection	x	x
Exit Slit Lamp Examination	x	x
Exit Snellen Distance Visual Acuity	x	x
Final Evaluation		x

### 7.2. Detailed Study Procedures

#### VISIT 1

Subjects will enter Visit 1 wearing their own form of vision correction.

Visit 1: Screening		
Step	Procedure	Details
1.1	Statement of Informed Consent	
Each subject must read, understand, and sign the Statement of Informed Consent before being enrolled into the study. The Principal Investigator or his/her designee conducting the informed consent discussion must also sign the consent form.
 
Note: The subject must be provided a signed copy of this document.

1.2	Demographics	Record the subject's year of birth, age, gender, race and ethnicity.
1.3	Medical History and Concomitant Medications	Record the subject's medical history and concomitant medications.
1.4	Habitual Lenses and Habitual Wear Time	Record the subject's habitual lens type, parameters, lens care solution, wear modality, approximate prescription date, and duration of lens wear.

**Clinical Study Protocol**  
**Johnson & Johnson Vision**

Visit 1: Screening		
Step	Procedure	Details
1.5	Eligibility after Screening	
All responses to Screening Inclusion Criteria questions must be answered “yes” and all responses to Exclusion Criteria must be answered “no” for the subject to be considered eligible.
 
If subject is deemed to be ineligible after screening, proceed to Final Evaluation and complete Subject Disposition. Refraction and Biomicroscopy forms do not need to be completed as part of Final Evaluation.

Visit 1: Baseline		
Step	Procedure	Details
1.6	Entrance Visual Acuity	Record the distance Snellen visual acuity (OD, OS, and OU) to the nearest letter with their habitual correction in place. Subjects must read the smallest line until at least 50% of the letters are read incorrectly.
1.7	Remove Habitual Lens	If applicable, the subject’s habitual contact lenses will be removed and stored in their own lens case. If they forgot to bring their lens case, one will be provided to them.
1.8	Subjective Spherocylindrical Refraction	
Complete subjective spherocylindrical refraction and record the resultant distance visual acuity (OD, OS, and OU) to the nearest letter.
 
Refractive cylinder guidelines:
 
 
• For sphere: 0.00 through 1.00 DC
 
• For multifocal: 0.00 through 0.75 DC
 
• For toric: 0.75 through 1.75 DC
 

1.9	ADD Power Determination (if applicable)	The near reading addition will be determined using the binocular crossed cylinder technique (BCC) at 40 cm.
1.10	ADD Power Refinement (if applicable)	Place the BCC result in the trial frame and refine the near prescription with trial lenses (or flippers) under binocular conditions. Subjects with at least a +0.75 D ADD will be fit with multifocal lenses. Otherwise fit with spherical lenses.

**Clinical Study Protocol**  
**Johnson & Johnson Vision**

Visit 1: Baseline			
Step	Procedure	Details	
1.11	Eye Dominancy	
The investigator will determine eye dominancy of the subject by first using the +1.00 blur test. If this fails to determine dominancy, then the sighting test will be used. See Appendix E.
	Appendix E
1.12	Iris Color	
The investigator will record the subject's iris color based on the scale provided.
	Appendix F
1.13	Slit Lamp Biomicroscopy	
FDA Slit Lamp Classification Scale will be used to grade the findings.
 
If any of these slit lamp findings are grade 3 or higher, the subject may not continue at this time, but may return up to one additional time to determine eligibility. If discontinued a final examination must be completed.
 
If the clearance of the fluorescein needs to be expedited, preservative-free rewetting drops or saline may be instilled.
	
1.14	Lens Design Assignment	
Based on their subjective refraction, the investigator will note whether the subject will receive a spherical lens on both eyes (Phase 1 and 2), a multifocal lens on both eyes (Phase 1 and 2), or a toric lens on both eyes (Phase 2 only). See section 4.1.
	
1.15	Eligibility after Baseline	
All responses to Inclusion Criteria questions must be answered "yes" and all responses to Exclusion Criteria questions must be answered "no" for the subject to be considered eligible.
 
If subject is deemed to be ineligible after baseline, proceed to Final Evaluation and complete Subject Disposition. Refraction and Biomicroscopy forms do not need to be completed as part of Final Evaluation.
	

**Clinical Study Protocol**  
**Johnson & Johnson Vision**

Visit 1: Baseline		
Step	Procedure	Details
1.16	Lens Design Fitting Steps	
Please jump to the appropriate fitting section in the protocol depending on the lens design:
 
 
• For spherical lenses, proceed to step 1.17.
 
• For multifocal lenses, proceed to step 1.25
 
• For toric lenses, proceed to step 1.32
 

Visit 1: Spherical Lens Fitting: Phase 1 and 2		
Step	Procedure	Details
1.17	Lens Selection	
Assign the study lens (Test or Control) according to the randomization scheme provided by the biostatistician.
 
Select the contact lens power based on the vertex-corrected refraction.
 
Record the test condition.

1.18	Lens Insertion	
The Investigator or the subject inserts the study lenses. Record the time of lens insertion.
 
Check for lens damage under the slit lamp before proceeding with lens settling.
 
Replace damaged lenses if applicable.
 
Ensure the subject is given a Clinic-only Wear Patient Instruction Guide.

1.19	Lens Settling 1	Allow the study lenses to settle for a minimum of 5 minutes.
1.20	Subjective Best Sphere Over Refraction	Perform subjective best sphere refraction over the study lenses with a phoropter (adopt the maximum plus to maximum visual acuity (MPMVA) approach) and record the best corrected distance visual acuity to the nearest letter (OD, OS, and OU).
1.21	Lens Power Modification (if applicable)	
Adjust the lens power if the subject's best sphere over-refraction is not plano. For each power modification, select the adjusted fitting lens power as appropriate and repeat steps 1.17 through 1.19.
 
Up to two power modifications are allowed.

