**Clinical Study Protocol**  
**Johnson & Johnson Vision**

Visit 1: Toric Lens Fitting: Phase 2		
Step	Procedure	Details
1.35	Subjective Best Sphere Over Refraction	Perform subjective best sphere refraction over the study lenses with a phoropter (adopt the maximum plus to maximum visual acuity (MPMVA) approach) and record the best corrected distance visual acuity to the nearest letter (OD, OS, and OU).
1.36	Lens orientation	Measure the lens orientation in each eye.
1.37	Lens Power Modification (if applicable)	
Adjust the lens power if the subject's best sphere over-refraction is not plano. Additionally, for toric lenses, adjust the lens axis parameter if the settled lens orientation is such that a different axis would be more appropriate (use the LARS rule to determine the replacement lens axis).
 
For each power modification, select the adjusted fitting lens power as appropriate and repeat steps 1.33 through 1.36.
 
Up to two power modifications are allowed.

1.38	Lens Settling 2	Please wait a total of 10 minutes from final lens insertion to continue.
1.39	Visual Acuity	Record the best corrected Snellen distance visual acuity to the nearest letter (OD, OS, and OU). Subjects must read the smallest line until at least 50% of the letters are read incorrectly. Visual acuity with the study contact lenses must be 20/30 or better OD, OS and OU.

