**Clinical Study Protocol**  
**Johnson & Johnson Vision**

Visit 2: Spherical Lens Fitting: Phase 1 and 2		
Step	Procedure	Details
2.6	Lens Selection	
Assign the study lens (Test or Control) according to the randomization scheme provided by the biostatistician.
 
Select the contact lens power based on the vertex-corrected refraction or the final powers from Visit 1.
 
Record the test condition.

2.7	Lens Insertion	
The Investigator or the subject inserts the study lenses. Record the time of lens insertion.
 
Check for lens damage under the slit lamp before proceeding with lens settling.
 
Replace damaged lenses if applicable.
 
Ensure the subject is given a Patient Instruction Guide.

2.8	Lens Settling 1	Allow the study lenses to settle for a minimum of 5 minutes.
2.9	Subjective Best Sphere Over Refraction	Perform subjective best sphere refraction over the study lenses with a phoropter (adopt the maximum plus to maximum visual acuity (MPMVA) approach) and record the best corrected distance visual acuity to the nearest letter (OD, OS, and OU).
2.10	Lens Power Modification (if applicable)	
Adjust the lens power if the subject's best sphere over-refraction is not plano. For each power modification, select the adjusted fitting lens power as appropriate and repeat steps 2.6 through 2.9.
 
Up to two power modifications are allowed.

2.11	Lens Settling 2	Please wait a total of 10 minutes from final lens insertion to continue.
2.12	Visual Acuity	Record the best corrected Snellen distance visual acuity to the nearest letter (OD, OS, and OU). Subjects must read the smallest line until at least 50% of the letters are read incorrectly. Visual acuity with the study contact lenses must be 20/30 or better OD, OS and OU.

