**Clinical Study Protocol**  
**Johnson & Johnson Vision**

Visit 2: Toric Lens Fitting: Phase 2		
Step	Procedure	Details
2.23	Lens Settling 1	Allow the study lenses to settle for a minimum of 5 minutes. For toric lenses, ensure the lens orientation has stabilized before continuing.
2.24	Subjective Best Sphere Over Refraction	Perform subjective best sphere refraction over the study lenses with a phoropter (adopt the maximum plus to maximum visual acuity (MPMVA) approach) and record the best corrected distance visual acuity to the nearest letter (OD, OS, and OU).
2.25	Lens orientation (toric lenses only)	If fitting toric lenses, measure the lens orientation in each eye.
2.26	Lens Power Modification (if applicable)	
Adjust the lens power if the subject's best sphere over-refraction is not plano. Additionally, for toric lenses, adjust the lens axis parameter if the settled lens orientation is such that a different axis would be more appropriate (use the LARS rule to determine the replacement lens axis).
 
For each power modification, select the adjusted fitting lens power as appropriate and repeat steps 2.24 through 2.27.
 
Up to two power modifications are allowed.

2.27	Lens Settling 2	Please wait a total of 10 minutes from final lens insertion to continue.
2.28	Visual Acuity	Record the best corrected Snellen distance visual acuity to the nearest letter (OD, OS, and OU). Subjects must read the smallest line until at least 50% of the letters are read incorrectly. Visual acuity with the study contact lenses must be 20/30 or better OD, OS and OU.

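### For sphere wearers, the Visit 1 power-change loop omits the repeat over-refraction that Visit 2 includes, so a changed Visit 1 lens is not verified as plano before the primary test; the toric loop at step 2.26 and Table 5 need matching corrections

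*Combined protocol and SAP*

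**What the plan says.** Section 4.1 implies a refractive target for two of the three designs. It says that multifocal lenses "will not follow the same 0.00 D over-refraction requirement as the spherical and toric designs".

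Section 7.2 puts this into practice. The trigger is the same in the sphere and toric power-modification steps that can be read, at both visits: "Adjust the lens power if the subject's best sphere over-refraction is not plano". So is the limit: "Up to two power modifications are allowed". The loops that follow a power change differ:

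- Sphere, Visit 1, step 1.21: "select the adjusted fitting lens power as appropriate and repeat steps 1.17 through 1.19".
- Sphere, Visit 2, step 2.10: "select the adjusted fitting lens power as appropriate and repeat steps 2.6 through 2.9".
- Toric, Visit 1, step 1.37: "repeat steps 1.33 through 1.36".
- Toric, Visit 2, step 2.26: "repeat steps 2.24 through 2.27".

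After fitting, the remaining vision check before psychophysical testing is an acuity of 20/30 or better, at both visits.

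In Table 5 (Section 7.1), the row that begins "Lens Power Modification (if applicable" is marked at Visit 1 only. So are the rows for lens selection, lens insertion and settling, and toric fit. The row for visual acuity and over-refraction is marked at both visits.

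**The concern.** Sphere visual range is one of the two primary comparisons. It is read binocularly at 8 cycles per degree, and each subject's Test and Control lenses are worn at different visits. The paired comparison is cleanest if both lenses pass the same refractive check before testing.

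Under step 1.21 as written, a sphere lens whose power was changed at Visit 1 is inserted and settled but not over-refracted again. The second modification that the same step allows then has no measurement to trigger it. The later 20/30 criterion is a coarse pass/fail gate and does not test for plano. Visit 2 may start from the final Visit 1 powers (step 2.6) and always measures over-refraction (step 2.9). A residual error missed at Visit 1 could therefore be found and removed at Visit 2, which would leave the two halves of one subject's pair in different refractive states.

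**Working it through.** **Step tracing.** Each loop is set against the steps it covers.

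| Loop | Range repeated | Contents | Insertion repeated | Over-refraction repeated |
|---|---|---|---|---|
| Sphere V1, 1.21 | 1.17 to 1.19 | selection, insertion, settling 1 | yes | no (1.20 is outside) |
| Sphere V2, 2.10 | 2.6 to 2.9 | selection, insertion, settling 1, over-refraction | yes | yes (2.9) |
| Toric V1, 1.37 | 1.33 to 1.36 | insertion, settling 1, over-refraction, orientation | yes | yes (1.35) |
| Toric V2, 2.26 | 2.24 to 2.27 | over-refraction, orientation, 2.26 itself, settling 2 | no (2.22 is outside) | yes (2.24) |

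The two sound loops (2.10 and 1.37) both end on the step just before the modification step. Step 1.21 stops one short of that. Step 2.26 starts two steps late and runs two past it; 2.22 to 2.25 would match 1.37 item for item. This pattern suggests numbering slips rather than intent.

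The Table 5 rows unmarked at Visit 2 correspond to steps that exist there: selection (2.6, 2.21), insertion and settling (2.7 and 2.8, 2.22 and 2.23), power modification (2.10, 2.26) and toric fit (2.30).

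**The plan's power figure.** Table 9 gives, for sphere visual range, an SD of paired differences of 0.10, effect size 1.83, alpha 0.05, power 0.94 and n = 6. Section 14.2 specifies an exact paired t-test at one-sided 0.025, which is equivalent to the tabulated two-sided 0.05 here. Power comes from the noncentral t with n − 1 degrees of freedom and noncentrality effect size × √n. At n = 6 the noncentrality is 1.83 × √6 = 4.48 and power is 0.9425. The plan's 0.94 is reproduced.

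**Room for added noise at 40 completers.** The planned difference is 1.83 × 0.10 = 0.183 LRE. Holding it fixed and inflating the SD gives:

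| SD multiplier | Effect size | Power at n = 40 |
|---|---|---|
| 2 | 0.915 | above 0.999 |
| 3 | 0.61 | 0.964 |
| 3.5 | 0.523 | 0.897 |
| 4 | 0.458 | 0.806 |

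Power reaches 90% at an effect size of 0.526, that is, at an SD of 0.183 / 0.526 = 0.348, or about 3.5 times the planned value. If fitting noise were independent of the other variation, its own SD across all subjects would have to be √(0.348² − 0.10²) = 0.333 LRE. That is about 1.8 times the planned Test-Control difference (0.333 / 0.183).

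**Effect of a pure visit shift.** Let τ be Test minus Control and π an additive Visit 2 minus Visit 1 shift. The expected difference is τ − π in Test/Control subjects and τ + π in Control/Test subjects. The period-adjusted estimate averages the two sequence means: [(τ − π) + (τ + π)] / 2 = τ. Simulation with assumed shifts of 0.05 and 0.10 LRE left it at 0.183, even with sequences split 24/16. Only an unadjusted mean moves at 24/16: 0.183 − 0.05 × 8/40 = 0.173 and 0.183 − 0.10 × 8/40 = 0.163. The planned model (Section 14.5) includes period.

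**The case against.** The strongest reply is that these are cross-reference slips that a competent site would read through. After settling at 1.19 the next step is 1.20, and allowing two modifications makes sense only if the over-refraction is redone. The authors' intention is probably just that. But the instruction names an end point, and the Visit 2 sphere loop shows how the check is included when it is meant. Two fitters could reasonably do different things, and the ambiguity sits immediately before a primary measurement.

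It is also fair to say that any noise is probably in the planning SD already. The sphere fitting steps are headed for both phases, the synopsis says that Phase 2 follows the Phase 1 procedures, and the Table 9 assumptions come from Phase 1. This stands, and it is one more reason not to see a threat to power.

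Scope is limited too. The missing over-refraction concerns sphere wearers at Visit 1 whose first over-refraction was not plano, a share that the documents do not give. Both toric loops repeat the over-refraction, a changed toric lens must physically be inserted whatever the range says, and toric endpoints are exploratory. The Visit 1 multifocal steps contain no power modification, and Section 4.1 exempts that design from 0.00 D. Multifocal steps 2.14 to 2.19 are not in the text available for review, so nothing is concluded about them.

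**Conclusion.** The inconsistency is real and worth correcting, but its consequence is modest. For sphere wearers, step 1.21 conflicts with its own second modification, with the requirement in Section 4.1 and with step 2.10. Step 2.26 and Table 5 conflict with their counterparts. The likely result is a small, unquantified increase in within-subject noise among subjects whose power is changed. Sample size, alpha and stated power are unaffected.

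Three stronger readings are tempting, and the documents do not support them.

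- A reader might infer that a subject's two lenses are not brought to the same refractive endpoint. Both visits perform an over-refraction, aim for plano and allow two changes. What is missing is re-verification after a change at Visit 1.
- A reader might take Table 5 to mean that power is not adjusted at Visit 2. The table also omits Visit 2 lens selection and insertion, without which the visit could not take place. It is an incomplete schedule, and the detailed steps provide for the adjustment.
- A reader might infer bias, or work out a loss in visual range from an assumed defocus. An additive visit effect drops out of the period-adjusted comparison. A shift that differed by lens would not drop out fully, but nothing in the documents points to one: Tables 1 and 2 list the same base curve, diameter and powers for the two sphere lenses. The documents give no conversion from dioptres to LRE and no residual error after correction, and the non-presbyopic wearers in this group (aged 18 to 39) may accommodate.

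One case deserves mention. Section 14.5 restricts the analysis to period 1 if the sequence effect is significant. The sphere result would then rest entirely on the visit that lacks the check, and without within-subject pairing. Both lenses would have been fitted under the same loop, so this too is a matter of precision rather than bias.

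**What to change.** Reconcile the passages so that the same over-refraction check follows any power change at both visits:

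- Step 1.21: extend the repeated range to include step 1.20.
- Step 2.26: align the range with step 1.37, so that it runs from insertion through orientation (2.22 to 2.25).
- Table 5: mark lens selection, lens insertion and settling, power modification (if applicable) and toric fit (if applicable) at Visit 2.

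The cost is two step references, four table marks, and a few minutes for a repeat over-refraction in Visit 1 sphere wearers whose power was changed. No visit is added, and the sample size, alpha and analysis model stay as they are.
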